### 17.1 Sample size calculation

The primary objective of this trial is to confirm the efficacy of IDegLira in controlling glycaemia as assessed by change from baseline in  $HbA_{1c}$  after 26 weeks of treatment vs. IDeg and liraglutide, respectively. This is done by comparing the difference in change from baseline in  $HbA_{1c}$  after 26 weeks of treatment to a non-inferiority margin of 0.4% for IDegLira vs. IDeg and to a superiority margin of 0.0% for IDegLira vs. liraglutide. The non-inferiority margin of 0.4% (absolute) was chosen in accordance with the Food and Drug Administration (FDA) guidance  $\frac{14}{2}$ .

A hierarchical testing procedure is applied. This is based on an a priori ordering of the null-hypotheses and testing them in this order using the two-sided 95% confidence interval approach until an insignificant result appears. Non-inferiority and superiority will thus be considered confirmed if the upper bound of the two-sided 95% confidence interval is below 0.4% and 0.0% respectively. This is equivalent to using a one-sided test of size 2.5%, which means that the type 1 error rate is controlled at 2.5%.

Formally, let D be the mean difference in change from baseline in  $HbA_{1c}$ . The null-hypothesis are given as

- Non-inferiority:  $H_0$  D $\geq$ 0.40% against  $H_A$  D<0.40%, with an assumed mean difference in treatment of 0.0% and a standard deviation of 1.0%
- Superiority: H0 D≥0.0% against HA D<0.0%, with an assumed mean difference in treatment of -0.3% and a standard deviation of 1.0%

Protocol Trial ID: NN9068-4148 UTN: U1111-1154-6671	CONFIDENTIAL	Date: Version: Status: Page:	07 October 2014 2.0 Final 61 of 84	
---	--------------	---------------------------------------	---	--

For evaluation of non-inferiority the PP-population is used for the sample size calculations, while the FAS is used for evaluation of superiority. It is assumed that 15% of the randomised subjects will be excluded from the PP analysis set. The above assumptions are based on experience from the phase 3a development programmes for IDegLira and IDeg. The sample size is determined using a t-statistic under the assumption of a one-sided test of size 2.5% for both the superiority and non-inferiority testing. Based on these assumptions a sample size of 720 patients results in a non-inferiority power of 98.1% and a superiority power of 90.7% i.e. the combined power for meeting the primary objective is 98.1% \* 90.7% = 89.0%. A sample size of 720 patients with a 15% drop-out rate and a 2:1:1 randomisation results in 306 PP patients in the IDegLira arm.

### 17.2 Definition of analysis sets

The following analysis sets are defined in accordance with the ICH-E9 guidance $\frac{15}{2}$ .

- Full Analysis Set (FAS): includes all randomised subjects. In exceptional cases, subjects may be eliminated from the full analysis set. In such cases the elimination will be justified and documented. The statistical evaluation of the FAS will follow the intention-to-treat (ITT) principle and subjects will contribute to the evaluation "as randomised"
- **Per-Protocol (PP) analysis set:** includes all subjects in the Full Analysis Set who fulfils the following criteria:
  - Have not violated any inclusion criteria
  - o Have not fulfilled any exclusion criteria
  - Have a non-missing HbA1c at screening or randomisation
  - o Have at least one non-missing HbA1c after 12 weeks of exposure
  - Have at least 12 weeks of exposure

Subjects will contribute to the evaluation "as treated".

- Safety Analysis Set (SAS): includes all subjects receiving at least one dose of the investigational product or comparator. Subjects in the safety set will contribute to the evaluation "as treated"
- Completer Analysis Set (CAS): includes all randomised subjects who have completed the trial. Subjects in the completer analysis set will contribute to the evaluation "as randomised"

Protocol Trial ID: NN9068-4148 UTN: U1111-1154-6671	CONFIDENTIAL	Date: Version: Status: Page:	07 October 2014 2.0 Final 62 of 84	Novo Nordisk
---	--------------	---------------------------------------	---	--------------

Randomised subjects who are lost to follow up and where no exposure information of the investigational product or comparators is available after randomisation will be handled as unexposed.

Before data are released for statistical analysis, a review of all data will take place to identify protocol deviations that could potentially affect the results. Any decision to exclude any subject or observation from the statistical analysis is the joint responsibility of the members of the study group. The subjects or observations to be excluded, and the reasons for their exclusion must be documented and signed by those responsible before database lock. The subjects and observations excluded from analysis sets, and the reason for this, will be described in the clinical trial report.

### 17.3 Primary endpoint

The primary endpoint is defined as change from baseline in HbA1c after 26 weeks of treatment.

The change from baseline in  $HbA_{1c}$  after 26 weeks of treatment will be analysed using an ANCOVA model with treatment and previous OAD treatment (metformin  $\pm$  one other OAD) as fixed effects and baseline  $HbA_{1c}$  as covariate. Missing values after 26 weeks of treatment will be imputed applying LOCF using  $HbA_{1c}$  values at and after baseline.

Non-inferiority of IDegLira vs. IDeg will be considered as confirmed if the 95% confidence interval for the mean treatment difference lies entirely below 0.4%; equivalent to a one-sided test with significance level of 2.5%. Non-inferiority will be investigated on the FAS. Sensitivity analysis will be performed on the PP analysis set.

Superiority of IDegLira vs. liraglutide will be considered as confirmed if the 95% confidence interval for the mean treatment difference for change from baseline in  $HbA_{1c}$  lies entirely below 0.0%; equivalent to a one-sided test with significance level of 2.5%. Conclusion of superiority will be based on FAS. The primary objective will be fulfilled only if both non-inferiority of IDegLira vs. IDeg and superiority of IDegLira vs. liraglutide are confirmed.

In addition to the non-inferiority margin of 0.4% the upper bound of the confidence interval for the mean treatment difference of IDegLira vs. IDeg will also be compared to a 0.0% margin. This comparison is not part of the hierarchical testing procedure.

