### 5.2 Rationale for trial design

Based on prior experience from IDegLira trials, the treatment duration of 26 weeks is sufficient to reach a stable HbA1c level, and to obtain sufficient data for efficacy and safety evaluation. The parallel design has been chosen instead of a cross-over design to avoid the risk of carry-over effect and to keep the treatment period as short as possible.

An open label design has been chosen due to two different regimens; fixed dose treatment of liraglutide with a maximal recommended dose of 1.8 mg/mL per day and treat-to-target for the IDeg and IDegLira arms. For the IDegLira treatment arm the maximal dose is 50 dose-steps per day since this will contain the liraglutide component maximal recommended dose of 1.8 mg/mL per day. Blinding of the trial by use of double dummy design would mean an unacceptable number of injections, increase the complexity and thereby introduce an increased risk of non-compliance or withdrawal.

To obtain improved HbA1c results the TTT approach has been chosen in order to ensure optimal treatment with frequent visits and titration of IDeg and IDegLira based on pre-breakfast self-measured plasma glucose (SMPG) values.

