# 17 Statistical considerations

Novo Nordisk will analyse and report data from all sites together.

All analyses of efficacy and safety endpoints will be based on the full analysis set (FAS). The analysis of the primary endpoint will be repeated on the per-protocol (PP) analysis set and the completer analysis set (CAS) for sensitivity purposes. All efficacy endpoints will be summarised using the FAS and safety endpoints will be summarised using the safety analysis set (SAS).

The impact of protocol deviations and outliers may be investigated further in sensitivity analyses if deemed relevant.

Unless otherwise specified, all continuous measurements will be summarised descriptively at each visit by treatment using observed data. After 26 weeks of treatment, descriptive statistics will be presented based both on observed and last observation carried forward (LOCF) imputed data. Endpoints that are analysed untransformed and endpoints that are not formally analysed are summarised by the arithmetic mean, standard deviation (SD), median, and minimum and maximum value. Endpoints that are analysed log-transformed are supplemented with the geometric mean and coefficient of variation (CV).

For measurements over time, mean values will be plotted to explore the trajectory over time. LOCF imputed data will be used as the basis for plotting data, if not otherwise specified. For endpoints that are analysed log-transformed, the geometric mean values will be plotted.

A standard analysis of covariance (ANCOVA) model will be applied for the continuous primary and secondary endpoints. The model includes treatment and previous OAD treatment (metformin or metformin in combination with one of the following: AGI, SU, glinides and TZD as fixed effects and the corresponding baseline value as covariate. In the following, this model will be referred to as the standard ANCOVA model.

Presentation of results from a statistical analysis will include the estimated mean treatment effects (Least Square Means [LSMeans]) for absolute values and change from baseline. In addition, estimated mean treatment difference (or ratio) will be presented together with the two-sided 95% confidence interval and corresponding two-sided 5% p-value.

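### The primary ANCOVA names no protection against unequal arm variances, so the stated one-sided 2.5% level is not assured in this 2:1:1 trial

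*Protocol*

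**What the plan says.** Section 17 of the protocol sets the general model: "A standard analysis of covariance (ANCOVA) model will be applied for the continuous primary and secondary endpoints". Section 17.3 applies it to the primary endpoint, which "after 26 weeks of treatment will be analysed using an ANCOVA model with treatment and previous OAD treatment" as fixed effects, with baseline HbA1c as covariate. Neither section mentions a variance that differs by arm or a robust standard error.

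Both primary decisions rest on the interval from this model. Non-inferiority to IDeg "will be considered as confirmed if the 95% confidence interval for the mean treatment difference lies entirely below 0.4"%, and superiority to liraglutide requires the interval to lie below zero. Section 17.1 says of this rule: "This is equivalent to using a one-sided test of size 2.5%, which means that the type 1 error rate is controlled at 2.5"%. The amendment of 28 September 2016 edited this sentence only to add that the level is one-sided.

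Allocation is 2:1:1 with 720 subjects (sections 5.1 and 6.1). On the regimens, section 5.2 says: "An open label design has been chosen due to two different regimens", namely fixed-dose liraglutide and treat-to-target IDeg and IDegLira. Planning uses the same SD for both comparisons: "with an assumed mean difference in treatment of 0.0% and a standard deviation of 1.0"% for non-inferiority and "with an assumed mean difference in treatment of -0.3% and a standard deviation of 1.0"% for superiority (section 17.1).

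**The concern.** A pooled residual variance gives the right standard error for a contrast when the arms share one variance. With unequal arm sizes it can be too small or too large when they do not, and 360:180:180 is unequal.

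The protocol gives reasons why the spread might differ by arm. Two arms are titrated to a fasting glucose target and one is held at a fixed dose. Of the titrated arms, IDegLira has a dose cap and IDeg has none (Appendix A, section 2). Subjects above hyperglycaemia limits are withdrawn (section 6.4) and their last value is carried forward (section 17), so differing withdrawal would also affect the spread.

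At stake is the level of the confirmatory tests. The primary objective needs both tests to succeed. If non-inferiority to IDeg is clearly true, the false-positive risk of the whole objective is close to that of the superiority test against liraglutide. Passing both also opens the confirmatory secondary tests (section 17.4.1). The planned sensitivity analyses do not cover this: the per-protocol and completer analyses repeat the same model, and the MMRM covariance is unstructured over visits but is not said to differ by arm (section 17.3.1).

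**Working it through.** **Inputs from the protocol.** 720 subjects at 2:1:1 give 360/180/180 in the full analysis set, on which 17.3 decides both tests. With 15% excluded, the per-protocol set has 306/153/153. SD is 1.0%, the margin 0.4%, and the assumed differences 0.0% and -0.3%. The level is set "under the assumption of a one-sided test of size 2.5% for both the superiority and non-inferiority testing".

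**Assumption.** Arm-specific SDs are not given. They are varied below around 1.0.

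**1. The protocol's own powers.** Power = Φ(distance/SE - 1.96).
- Non-inferiority: SE = √(1/306 + 1/153) = 0.0990; 0.4/0.0990 - 1.96 = 2.08; power 98.1%.
- Superiority: SE = √(1/360 + 1/180) = 0.0913; 0.3/0.0913 - 1.96 = 1.33; power 90.8% (90.7% with the noncentral t).
- Product of the stated figures: 0.981 × 0.907 = 0.890.

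The stated 98.1%, 90.7% and 89.0% are therefore right under one common SD.

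**2. True size under unequal SDs.** Let a, b and l be the residual variances for IDegLira, IDeg and liraglutide.
- Pooled variance = (360a + 180b + 180l)/720.
- Model SE (either contrast) = √[pooled × (1/360 + 1/180)].
- True SE vs liraglutide = √(a/360 + l/180); vs IDeg = √(a/360 + b/180).
- One-sided size = 1 - Φ(1.96 × model SE / true SE).

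**3. Liraglutide SD 1.2, others 1.0.** Pooled variance = (540 + 180 × 1.44)/720 = 1.11, so the model SE = √(1.11 × 0.008333) = 0.0962.
- Superiority: true SE = √(0.002778 + 0.008) = 0.1038; ratio 0.926; 1.96 × 0.926 = 1.816; size 3.47%.
- Non-inferiority: true SE = 0.0913; ratio 1.053; size 1.95%.

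**4. Two-arm fit.** If each contrast is fitted on its own arms, the same SDs give a pooled variance of (360 + 180 × 1.44)/540 = 1.147 for superiority. The SE ratio is 0.942 and the size 3.25%. Non-inferiority stays at 2.50%.

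**5. Range.** One-sided size, superiority / non-inferiority:

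| SD IDegLira/IDeg/liraglutide | Three-arm fit | Two-arm fits |
|---|---|---|
| 1/1/1 | 2.50% / 2.50% | 2.50% / 2.50% |
| 1/1/1.1 | 2.98% / 2.22% | 2.88% / 2.50% |
| 1/1/1.2 | 3.47% / 1.95% | 3.25% / 2.50% |
| 1/1/1.3 | 3.95% / 1.69% | 3.60% / 2.50% |
| 1/1/0.8 | 1.60% / 3.08% | 1.75% / 2.50% |
| 1/1.2/1 | 1.95% / 3.47% | 2.50% / 3.25% |
| 1/1.2/1.2 | 2.85% / 2.85% | 3.25% / 3.25% |
| 1.2/1/1 | 2.16% / 2.16% | 1.87% / 1.87% |

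Only SD ratios enter the formula. The second figure of each pair therefore also applies to the body-weight contrast with IDeg at the same ratios.

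**6. Simulation.** The three-arm ANCOVA with baseline and previous OAD treatment was simulated with 20,000 runs per pattern (Monte Carlo error about 0.1 point). At 1/1/1.2 the pooled standard error gave 3.4% for superiority and 1.9% for non-inferiority. An HC2 standard error gave 2.6% and 2.5%. Over six patterns (1/1/1, 1/1/1.2, 1/1/1.5, 0.8/0.8/1.2, 0.8/1/1.2 and 1.2/1/1), HC2 kept both tests between 2.3% and 2.7%.

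**The case against.** The strongest reply is that the protocol contains no error here. It names a conventional ANCOVA, and its 2.5% is the nominal level of that model. Nothing in the document says that the arm variances differ, and the choice of standard error may sit in an analysis plan that is not shown. Much of this stands. Every size other than 2.5% comes from an assumed SD ratio, and at a ratio of 1.1 the excess is about half a percentage point. The reply does not remove the point, because the protocol itself fixes the deciding model and asserts control of the error rate without qualification.

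Fitting all three arms at once is stated only for the supportive efficacy endpoints (section 17.4.2.1) and is inferred for the primary. That is correct, but the superiority test remains liberal in a two-arm fit.

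A reader might infer three stronger claims, none of which is supported:
- **Both tests exceed their level.** If only liraglutide is more variable, the non-inferiority test is conservative or unchanged.
- **One test always becomes liberal as the other becomes conservative.** At 1/1.2/1.2 both are liberal; at 1.2/1/1 both are conservative.
- **The 2.5% holds only under equal variances.** In the three-arm fit, model and true SE for superiority agree whenever 5l = 2a + 3b, which includes unequal cases.

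**Conclusion.** The stated type 1 error control is not assured if the arms' residual variances differ, and no planned analysis relaxes the assumption. The leading case is a liraglutide SD 1.1 to 1.3 times that of the other arms: superiority at about 3.0% to 4.0% in a three-arm fit (2.9% to 3.6% in a two-arm fit), with non-inferiority conservative or unchanged. Equal SDs give exactly the stated level.

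This rests on the ordinary reading of the ANCOVA as having a single residual variance, on large-sample formulas supported by simulation, and on SD ratios that the documents do not supply. The documents do not show that the variances differ, or in which direction. It would therefore be wrong to read this as proof that the trial's tests miss their level. It is a worthwhile, inexpensive safeguard for a stated claim.

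**What to change.** In section 17.3, add that the 95% confidence intervals for the two treatment contrasts use a heteroscedasticity-consistent covariance (for example HC2 or HC3) with the same ANCOVA mean model, and that these intervals decide non-inferiority and superiority. Say the same for body weight in section 17.4.1. HC2 is the version simulated above. Fix the choice before data are reviewed, since the trial is open-label.

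Point estimates, sample size and testing hierarchy are unchanged. Arm-specific residual variances would be an alternative, but they reweight the fit and can move the adjusted estimates, so the robust covariance is the simpler change. The cost is one sentence, a software option and a negligible loss of precision if the variances are equal. It does not restore power: with liraglutide SD 1.2 and each arm's own variance, superiority power is Φ(0.3/0.1038 - 1.96) = 82.4%, against the planned 90.7%. That loss comes from the larger spread, not from the correction.

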### 17.3.1 Sensitivity analysis

The primary analysis will be repeated on the PP analysis set and the CAS as sensitivity analysis. Furthermore, sensitivity analysis will be performed on FAS using the mixed model for repeated measurement (MMRM) to evaluate the sensitivity of using LOCF. All HbA1c values available post baseline at scheduled measurement times will be analysed in a linear mixed normal model using an unstructured residual covariance matrix for HbA1c measurements within the same subject. The model will include treatment, visit, and previous OAD treatment as fixed effects and baseline

UTN: U1111-1154-6671	Protocol Trial ID: NN9068-4148 UTN: U1111-1154-6671	CONFIDENTIAL		**	Novo Nordisk
----------------------	---	--------------	--	----	--------------

HbA1c as covariate. Interactions between visit and all factors and the covariate are also included in the model. The result will be compared to the result of the ANCOVA method using LOCF for imputation of missing data. Any marked difference between the MMRM and ANCOVA LOCF approach regarding the estimated treatment difference will be commented upon in the CTR.

# 17.4 Secondary endpoints

# 17.4.1 Confirmatory secondary endpoints

The following two confirmatory endpoints will be tested for superiority of IDegLira vs. IDeg.

- Change from baseline in body weight after 26 weeks of treatment.
- Number of treatment emergent severe or BG confirmed hypoglycaemic episodes during 26 weeks of treatment

The tests for superiority of the confirmatory secondary endpoints will be based on the FAS and will only be carried out if non-inferiority of IDegLira vs. IDeg and superiority of IDegLira vs. liraglutide with regards to the primary endpoint are confirmed.

In order to control the overall type I error on a 5% level with regards to the secondary endpoints, a hierarchical testing procedure will be used. If superiority is confirmed with respect to change from baseline in body weight after 26 weeks of treatment the number of treatment emergent severe or BG confirmed hypoglycaemic episodes during 26 weeks of treatment will be tested for superiority. Superiority for change from baseline in body weight will be considered confirmed if the upper bound of the two-sided 95% confidence interval for the estimated mean treatment difference (IDegLira minus IDeg) is strictly below zero or equivalently if the p-value for the one-sided test of

 $H_0 D \ge 0.0\%$  against  $H_A D < 0.0\%$ ,

is less than 2.5%, where D is the treatment difference.

Superiority for hypoglycaemic episodes will be considered confirmed if the upper bound of the two-sided 95% confidence interval for the estimated mean treatment ratio (IDegLira vs. IDeg) is strictly below one or equivalently if the p-value for the one-sided test of

 $H_0$  RR $\geq$ 1.0 against  $H_A$  RR $\leq$ 1.0,

is less than 2.5%, where RR is the estimated rate ratio.

The change from baseline in body weight after 26 weeks of treatment will be analysed using an ANCOVA model with treatment and previous OAD treatment (metformin  $\pm$  one other OAD) as fixed effect and baseline weight as covariate.

Protocol Trial ID: NN9068-4148 UTN: U1111-1154-6671	CONFIDENTIAL	Date: Version: Status: Page:	07 October 2014 2.0 Final 64 of 84	
---	--------------	---------------------------------------	---	--

Number of treatment emergent severe or BG confirmed hypoglycaemic episodes during 26 weeks of treatment will be analysed using a negative binominal regression model with a log-link function and the logarithm of the time period in which a hypoglycaemic episode is considered treatment emergent as offset. The model will include treatment and previous anti-diabetic treatment as fixed factors and baseline HbA1c as covariate.

# 17.4.2 Supportive secondary endpoints

### 17.4.2.1 Efficacy endpoints

In the following the statistical models will be fitted to all data simultaneously (all treatment groups) and from this model the treatment differences for IDegLira vs. IDeg and IDegLira vs. liraglutide will be estimated.

### Insulin dose after 26 weeks of treatment

The actual daily insulin dose after 26 weeks of treatment will be analysed using an ANCOVA model including treatment and previous anti-diabetic treatment as fixed factors and baseline HbA1c value and baseline insulin dose as covariates.

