## 5 Trial design

### 5.1 Type of trial

This is a 26 week, randomised, parallel three-arm, open-label, multi-centre, treat-to-target (TTT) confirmatory trial in Chinese subjects with T2DM inadequately controlled with metformin  $\pm$  one other OAD:  $\alpha$ -glucosidase inhibitors (AGI), sulphonylureas (SU), glinides and thiazolidinediones (TZD). Inadequately controlled diabetes will be defined as a HbA $_{1c}$  level of 7.0-10% (both inclusive).

Subjects will be randomised in a 2:1:1 manner to receive IDegLira, IDeg or liraglutide all once daily (OD) in combination with metformin. Other pre-trial OAD treatment will be discontinued at randomisation. The randomisation of subjects to treatment groups will be stratified by previous treatment with metformin  $\pm$  one other OAD.

The duration of the trial from screening (Visit 1) to follow-up (Visit 29) will be approximately 29 weeks with treatment duration of 26 weeks. At the screening visit, eligibility of the subjects is determined followed by randomisation (Visit 2). One week after end of treatment (Visit 28), the follow-up (Visit 29) will be conducted.

The trial design is summarised schematically below.

[figure not shown]

Figure 5–1 Trial Design

 Protocol
 Date:
 07 October 2014
 Novo Nordisk

 Trial ID: NN9068-4148
 Version:
 2.0

 UTN: U1111-1154-6671
 Status:
 Final

Page:

20 of 84

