### 5.3 Treatment of subjects

Subjects treated with metformin ± one other OAD (AGI, SU, glinides or TZD) in accordance with the inclusion criterion are eligible for the trial. At randomisation subjects will have to discontinue all OADs except for metformin, leaving this at pre-trial dose in combination with one of the treatments for subcutaneous injection described below:

- 1. IDegLira added to current metformin therapy. Start dose will be 10 dose steps (10 U of IDeg and 0.36 mg of liraglutide) and will be titrated according to the Titration Guideline (appendix A) aiming for a FPG target of 4.0-5.0 mmol/L
- 2. IDeg added to current metformin therapy. Start dose will be 10 U and will be titrated according to the Titration Guideline aiming for a FPG target of 4.0-5.0 mmol/L
- 3. Liraglutide added to current metformin therapy. Start dose will be 0.6 mg and subsequent 0.6 mg weekly dose escalation to the target dose of 1.8 mg. If subjects are not able to tolerate the dose escalation as described above, the visit window may be used to prolong exposure time for a given dose. Liraglutide dose of 1.8 mg/day will be continued for the remaining part of the trial and at each site visit/telephone contact subjects must be asked to confirm their dose

The Titration Guideline contains more detailed guidance on switching from pre-trial treatment to trial products, timing of injection, and titration of these.

| Protocol | Date: 07 October 2014 | Novo Nordisk | Trial ID: NN9068-4148 | CONFIDENTIAL | Status: Final | Final |

Page:

21 of 84

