### 5.6 Rationale for treatment

Enrolment of insulin-naïve subjects with T2DM, inadequately controlled on 1-2 OADs, has been chosen to demonstrate the efficacy and safety of IDegLira, when added to metformin.

The rationale for including subjects with pre-trial treatment metformin ± one other OAD is to mimic common practice of diabetes treatment in subjects with T2DM failing on 1-2 OADs and will prevent undue heterogeneity of the treatment arms due to diverse treatment. The daily dose of metformin (≥ 1500 mg or max tolerated dose) is close to the maximum recommended dose as per local labelling for the treatment of type 2 diabetes.

When glycaemic control is not achieved or sustained on this background, the addition of another OAD, or initiation of GLP-1 receptor agonists, basal insulin or IDegLira can be considered.

The expected outcome after 26 weeks of treatment with IDegLira compared to IDeg is similar change in HbA1c, less weight gain, lower post-prandial glucose levels, and a lower rate of hypoglycaemic events. In comparison with liraglutide a greater decrease in HbA1c, a lower FPG level and fewer gastro intestinal AEs are anticipated for IDegLira. For more detailed information on IDegLira, please see Investigator's Brochure or any updates hereof.

IDeg and liraglutide have been included as comparators in order to comply with regulatory requirements to assess the risk benefit profile of the combination product as compared to the individual components.

Apart from metformin, other OADs are primarily excluded at randomisation because they are not approved for use combined with liraglutide and metformin by the CFDA and are also not supported by the China clinical programme for liraglutide in terms of safety (and efficacy).

Metformin treatment will be in accordance with locally approved label.

Date: 07 October 2014 | Novo Nordisk Protocol Trial ID: NN9068-4148 Version: 2.0 CONFIDENTIAL UTN: U1111-1154-6671 Final Status: 22 of 84

Page:

#### **Trial population** 6

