# **2** Treatment regimens

At randomisation all subjects will be randomised in a 2:1:1 manner into three parallel treatment groups:

- Insulin degludec/liraglutide (IDegLira) OD + metformin
- Insulin degludec (IDeg) OD + metformin
- Liraglutide OD + metformin

First dosing should take place on day of randomisation or on the day following randomisation.

Maximum dose for IDegLira is 50 dose steps (50 units of IDeg and 1.8 mg of liraglutide).

There is no maximum dose for IDeg.

There is no minimum dose for IDeg and IDeglira.

Instructions on the use of liraglutide have not been included in this guideline as no titration will take place. Instead, please refer to the protocol section 5.3 for instructions on start dose and dose escalation.

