#### 3.2 Titration

Dose will be adjusted twice weekly by the subject 3-4 days apart. The investigator will support titration at all contacts.

Titration should be performed based on the mean of three pre-breakfast self-measured plasma glucose (SMPG) values measured two days before and on day of titration. Titration should preferably be performed on the same days of the week throughout the trial. The dose adjustment will be performed according to Table 1.

Table 1 IDegLira and IDeg dose adjustment

Mean of three pre-breakfast SMPG values	Dose adjustment
mmol/L	U/Dose steps
<4.0	-2
4.0 – 5.0	No adjustment
> 5.0	+ 2

If one or more SMPG values are missing, the adjustment should be performed on the remaining SMPG value(s). However, the first time titration is performed after randomisation all three SMPG values must be available. If this is not the case, subjects must wait for the next titration day to adjust the dose.

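### The insulin-dose ANCOVA carries one residual variance although only the larger arm is capped at 50 dose steps, so its 95% interval is probably somewhat too narrow (minor)

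*Protocol*

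**What the plan says.** Insulin dose after 26 weeks is a supportive secondary efficacy endpoint (section 4.2.2.2), and insulin dose at end of treatment appears among the key efficacy assessments in the Summary. Its analysis is in section 17.4.2.1: "The actual daily insulin dose after 26 weeks of treatment will be analysed using an ANCOVA model". The amendment of 28 September 2016 restates this sentence and keeps the ANCOVA. The lead-in to the same section says that "the statistical models will be fitted to all data simultaneously (all treatment groups"), with IDegLira compared with IDeg and with liraglutide from that one fit. Insulin dose is not exempted. Section 17 promises a two-sided 95% interval and a p-value with each estimated difference.

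The dosing rules differ between the two insulin arms. Appendix A, section 2: "Maximum dose for IDegLira is 50 dose steps (50 units of IDeg and 1.8 mg of liraglutide"), and "There is no maximum dose for IDeg". Both arms start at 10 (section 5.3) and follow the same titration table: "Dose will be adjusted twice weekly by the subject 3-4 days apart", by 2 units or dose steps at a time (Appendix A, section 3.2). Allocation is 2:1:1 (section 5.1) of 720 subjects (section 6.1).

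**The concern.** An ordinary ANCOVA estimates one residual variance and applies it to every arm. Here the design itself makes the variances unequal: the cap compresses the upper end of the dose distribution in IDegLira and leaves IDeg free to spread. The compressed arm is twice the size of the other, so it dominates the pooled variance, while the true uncertainty of the difference comes mostly from the small, more variable IDeg arm. With unequal arms, that is the combination in which a pooled standard error is too small.

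Fitting all arms together adds a second problem. Liraglutide subjects receive no trial insulin. If they enter as zeros, 180 values without spread pull the common variance down further.

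At stake is the accuracy of one reported interval and p-value, for an endpoint that readers of a registration trial will look at. Nothing in the testing hierarchy depends on it.

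**Working it through.** **Arm sizes.** 720 in 2:1:1 gives 360 IDegLira, 180 IDeg and 180 liraglutide. The protocol states no figure for insulin dose that could be reproduced. Its HbA1c power figures do reproduce with these arm sizes (noncentral t, one-sided 2.5%, SD 1.0): non-inferiority 98.08% at 306:153 (stated 98.1%) and superiority 90.67% at 360:180 (stated 90.7%).

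**Reach of the titration.** At most +2 twice weekly from a start of 10: IDegLira can be at 50 after (50 − 10)/4 = 10 weeks. IDeg can rise to 10 + 4 × 26 = 114 U by week 26. The cap therefore has time to act.

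**Formula.** Let s1, s2 be the residual SDs in IDegLira and IDeg, and r = s2/s1.

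- Model-based variance of the difference: sp²(1/360 + 1/180), with sp² ≈ (2s1² + s2²)/3. This equals (2s1² + s2²)/360.
- True variance: s1²/360 + s2²/180 = (s1² + 2s2²)/360.
- SE ratio = √[(2 + r²)/(1 + 2r²)].
- Coverage = 2Φ(1.96 × SE ratio) − 1.

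Covariates are ignored; they would act on s1 and s2, not on the formula. An equal proportional loss of subjects in both arms leaves the ratio unchanged.

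| r | SE ratio | Coverage |
|---|---|---|
| 1.0 | 1.000 | 95.0% |
| 1.1 | √(3.21/3.42) = 0.969 | 94.2% |
| 1.5 | √(4.25/5.50) = 0.879 | 91.5% |
| 2.0 | √(6/9) = 0.816 | 89.0% |

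**Plausible r.** No dose SD is given, so this step is an assumption: log-normal dose need, the same in both arms, limited to 114 U by titration, and cut at 50 for IDegLira.

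| Mean, CV of need | At cap | SD IDegLira / IDeg | SE ratio | Coverage |
|---|---|---|---|---|
| 35 U, 0.35 | 11% | 9.8 / 12.2 | 0.931 | 93.2% |
| 35 U, 0.5 | 16% | 11.9 / 17.2 | 0.889 | 91.9% |
| 45 U, 0.5 | 32% | 11.2 / 21.2 | 0.827 | 89.5% |
| 55 U, 0.5 | 49% | 9.7 / 24.2 | 0.782 | 87.5% |
| 70 U, 0.35 | 79% | 4.3 / 21.7 | 0.727 | 84.6% |

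Over the grid the standard error is about 7 to 27% too small and coverage about 85 to 93%. A gamma distribution with means of 30 to 50 U and SDs of 15 to 30 U gives 88.8 to 93.5%. The result does not need identical dose need: with IDegLira needing 30 against 45 U, or 35 against 50 U, at CV 0.45, coverage is about 90%.

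**Liraglutide as zeros.** The residual sum of squares is unchanged, but the degrees of freedom rise from 538 to 717. The SE ratio is multiplied by √(538/717) = 0.866. With equal SDs in the two insulin arms, coverage is already only 91%. Over the log-normal grid it is about 78 to 89%.

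**What the cap contributes to the difference.** With identical need at CV 0.5, the cap alone produces a mean difference of about −2.5 U (mean 35), −6.3 U (mean 45) or −11.5 U (mean 55).

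**The case against.** **The variance structure belongs in the SAP, and the protocol says only ANCOVA.** Partly right. The SAP is not at hand and may already provide for unequal variances. But the protocol does fix the method and the all-groups fit, and ANCOVA without qualification means a common variance. Where another structure is wanted, for the repeated-measures model and the 9-point profile, the protocol says so. This supports a low severity but does not remove the point.

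**The size rests on assumed doses.** This stands. The 85% end needs a mean need of 70 U, with most IDegLira subjects at the cap, which nothing in the protocol supports. If few subjects reach 50 steps, the effect is negligible.

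**The endpoint is supportive.** This also stands. It carries no alpha and no power claim, and being listed as a key assessment does not change that.

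Three stronger readings are tempting and are not supported:

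- A reader might infer that the cap biases the estimated difference. The endpoint is actual dose, and the cap is part of the IDegLira regimen, so the difference in actual dose is estimated without bias. Nor does the protocol claim insulin sparing: dose is not among the outcomes that section 5.6 expects against IDeg.
- A reader might want IDeg doses cut at 50 before a difference is accepted. That replaces real doses and hides real effects: at mean 55 U and CV 0.5, a true 20% lower need (11 U) shrinks to about −4.6 U.
- A reader might attack baseline insulin dose as a covariate, since section 5.6 describes the subjects as insulin-naïve. The 2016 amendment reports an updated dose model and ends this sentence with a singular covariate, while deletion marks are not visible in the text available. The term may already be gone. Putting body weight in its place would be a preference, not a correction.

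**Conclusion.** The point holds as a conditional one, of minor severity. The cap, the 2:1 arm sizes and the common-variance model together put the larger variance in the smaller arm, and the direction of the error follows from the design. Its size depends on the share of IDegLira subjects at 50 steps. Under need of mean 35 to 70 U and CV 0.35 to 0.5 in both arms, coverage is about 85 to 93% in place of 95%; at an SD ratio of 1.1 or less it is about 94% or more. Zeros from the liraglutide arm would lower it to about 78 to 89% over the same range; whether they are meant to enter is unclear, and a literal reading of section 17.4.2.1 allows it. The point estimate, the sample size and every confirmatory conclusion are unaffected.

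**What to change.** In section 17.4.2.1, under insulin dose:

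1. State that this endpoint is fitted to IDegLira and IDeg only, as an exception to the all-groups sentence.
2. Use arm-specific residual variances or a robust variance estimator for the difference and its 95% interval.
3. Report the percentage of IDegLira subjects at 50 dose steps after 26 weeks, so that the difference is read as reflecting the cap as well as dose need.

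If the SAP already does this, aligning the protocol wording is enough. The cost is two sentences and one table line. When the variances are in fact equal, the separate variances cost practically no precision. Dosing and data collection do not change.
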